15.6 Reporting of Pregnancy

Although pregnancy is not considered an adverse event, it is the responsibility of investigators or their designees to report any pregnancy or lactation in a subject, including the pregnancy of a male subject's female partner as an SAE. Pregnancies or lactation that occurs during the course of the trial or with 30 days of completing the trial or starting another new anticancer therapy, whichever is earlier, must be reported to the DSMC, IRB, FDA, and the sponsor as applicable. All subjects and female partners who become pregnant must be followed to the completion/termination of the pregnancy. Pregnancy outcomes of spontaneous abortion, missed abortion, fetal death, intrauterine death, miscarriage, and stillbirth must be reported as serious events.

15.7 Protocol Amendments

Any amendments or administrative changes in the research protocol during the period, for which the IRB approval has already been given, will not be initiated without submission of an amendment for IRB review and approval.

These requirements for approval will in no way prevent any immediate action from being taken by the investigator in the interests of preserving the safety of all patients included in the trial.

Any amendments to the protocol that significantly affect the safety of subjects, scope of the investigation, or the scientific quality of the study are required to submit the amendment for FDA review.

15.8 Protocol Deviations

A protocol deviation (or violation) is any departure from the defined procedures and treatment plans as outlined in the protocol version submitted and previously approved by the IRB. Protocol deviations have the potential to place participants at risk and can also undermine the scientific integrity of the study thus jeopardizing the justification for the research. Protocol deviations are unplanned and unintentional events.

Because some protocol deviations pose no conceivable threat to participant safety or scientific integrity, reporting is left to the discretion of the PI within the context of the guidelines below. The IRB requires the **prompt reporting** of protocol deviations which are:

- Exceptions to eligibility criteria.
- Intended to eliminate apparent immediate hazard to a research participant or
- Harmful (caused harm to participants or others, or place them at increased risk of harm - including physical, psychological, economic, or social harm), or
- Possible serious or continued noncompliance

15.9 FDA Annual Reporting

An annual progress report will be submitted to the FDA within 60 days of the anniversary of the date that the IND went into effect. (21 CFR 312.33).

15.10 Clinical Trials Data Bank

The study will be registered on <http://clinicaltrials.gov> and the NCI CTRP (Clinical Trials Reporting Program) by the Clinical Trials Office.

15.11 Record Keeping

Per 21 CFR 312.57, Investigator records shall be maintained for a period of 2 years following the date a marketing application is approved; or, if no application is filed or the application is not approved, until 2 years after the investigation is discontinued and the FDA is notified.

17 APPENDIX

17.1 PROMIS-29 Questionnaire

RROPE

PROMIS-29 Questionnaire

Patient Study ID: 102312-01-_____

Patient Initials: _____

Date of Completion: _____ / _____ / _____

PROMIS-29 Profile v1.0

Please respond to each question or statement by marking one box per row.

Physical Function		Without any difficulty	With a little difficulty	With some difficulty	With much difficulty	Unable to do
		1	Are you able to do chores such as vacuuming or yard work?			
2	Are you able to go up and down stairs at a normal pace?					
3	Are you able to go for a walk of at least 15 minutes?					
4	Are you able to run errands and shop?					
Anxiety		Never	Rarely	Sometimes	Often	Always
5	In the past 7 days... I felt fearful					
6	I found it hard to focus on anything other than my anxiety					
7	My worries overwhelmed me					
8	I felt uneasy					
Depression		Never	Rarely	Sometimes	Often	Always
9	In the past 7 days... I felt worthless					
10	I felt helpless					
11	I felt depressed					
12	I felt hopeless					
Fatigue		Not at all	A little bit	Somewhat	Quite a bit	Very much
13	During the past 7 days... I feel fatigued					
14	I have trouble starting things because I am tired					
In the past 7 days...		Not at all	A little bit	Somewhat	Quite a bit	Very much
15	How run-down did you feel on average? ...					
In the past 7 days...		Not at all	A little bit	Somewhat	Quite a bit	Very much
16	How fatigued were you on average?					

PROMIS-29 Profile v1.0

Sleep Disturbance						
In the past 7 days...		Very poor	Poor	Fair	Good	Very good
17	My sleep quality was.....					
In the past 7 days...		Not at all	A little bit	Somewhat	Quite a bit	Very much
18	My sleep was refreshing.....					
19	I had a problem with my sleep.....					
20	I had difficulty falling asleep.....					
Satisfaction with Social Role						
In the past 7 days...		Not at all	A little bit	Somewhat	Quite a bit	Very much
21	I am satisfied with how much work I can do (include work at home).....					
22	I am satisfied with my ability to work (include work at home).....					
22	I am satisfied with my ability to do regular personal and household responsibilities.....					
24	I am satisfied with my ability to perform my daily routines.....					
Pain Interference						
In the past 7 days...		Not at all	A little bit	Somewhat	Quite a bit	Very much
25	How much did pain interfere with your day to day activities?.....					
26	How much did pain interfere with work around the home?.....					
27	How much did pain interfere with your ability to participate in social activities?.....					
28	How much did pain interfere with your household chores?.....					
Pain Intensity						
In the past 7 days...						
29	How would you rate your pain on average?.....					
		0 No pain	1	2	3	4
			5	6	7	8
			9	10		
						Worst imaginable pain

Appendix 17.2 EPIC Questionnaire

EPIC

The Expanded Prostate Cancer Index Composite

This questionnaire is designed to measure Quality of Life issues in patients with Prostate cancer. To help us get the most accurate measurement, it is important that you answer all questions honestly and completely.

Remember, as with all medical records, information contained within this survey will remain strictly confidential.

Today's Date (please enter date when survey completed): Month _____ Day _____ Year _____

Name (optional): _____

Date of Birth (optional): Month _____ Day _____ Year _____

1. In general, would you say your health is:

Excellent.....	1
Very good.....	2
Good.....	3
Fair.....	4
Poor.....	5

(Circle one number)

11/

2. The following questions are about activities you might do during a typical day.
Does your health now limit you in these activities? If so, how much?

(Circle 1, 2, or 3 on each line)

	Yes Limited A Lot	Yes, Limited A Little	No, Not Limited At All	
a. Moderate activities, such as moving a table, pushing a vacuum cleaner, bowling, or playing golf.....	1	2	3	12/
b. Climbing several flights of stairs.....	1	2	3	13/

3. During the **PAST 4 WEEKS**, have you had any of the following problems with your work or other regular daily activities as a result of your PHYSICAL HEALTH?

(Please answer YES or NO for each question by circling 1 or 2 on each line.)

	Yes	No	
a. Accomplished less than you would like	1	2	14/
b. Were limited in the kind of work or other activities	1	2	15/

4. During the **PAST 4 WEEKS**, have you had any of the following problems with your work or other regular daily activities as a result of any EMOTIONAL PROBLEMS, such as feeling depressed or anxious?

(Please answer YES or NO for each question by circling 1 or 2 on each line)

	Yes	No	
a. Accomplished less than you would like	1	2	16/
b. Didn't do work or other activities as carefully as usual	1	2	17/

5. During the past 4 weeks, how much did pain interfere with your normal work
(including both work outside the home and housework)?

Not at all 1
Slightly 2
Moderately 3 (Circle one number)
Quite a bit 4
Extremely 5

18/

6. These questions are about how you feel and how things have been with you during
the PAST 4 WEEKS. For each question, please give the one answer that comes
closest to the way you have been feeling. How much of the time during the past 4 weeks...

(Circle one number on each line)

All of the Time	Most of the Time	A Good Bit of the Time	Some of the Time	A Little of the Time	None of the Time
--------------------------	---------------------------	------------------------------------	---------------------------	----------------------------------	---------------------------

a. Have you felt calm and peaceful? 1 2 3 4 5 6 19/
b. Did you have a lot of energy? 1 2 3 4 5 6 20/
c. Have you felt downhearted and blue? 1 2 3 4 5 6 21/

7. During the past 4 weeks, how much of the time has your physical health or emotional
problems interfered with your social activities (like visiting with friends, relatives, etc.)?

22/

All of the time 1
Most of the time 2
Some of the time 3 (Circle one number)
A little of the time 4
None of the time 5

URINARY FUNCTION

This section is about your urinary habits. Please consider **ONLY THE LAST 4 WEEKS**.

8. Over the past 4 weeks, how often have you leaked urine?

More than once a day.....	1
About once a day.....	2
More than once a week.....	3
About once a week.....	4
Rarely or never.....	5

23/

9. Over the past 4 weeks, how often have you urinated blood?

More than once a day.....	1
About once a day.....	2
More than once a week.....	3
About once a week.....	4
Rarely or never.....	5

24/

10. Over the past 4 weeks, how often have you had pain or burning with urination?

More than once a day.....	1
About once a day.....	2
More than once a week.....	3
About once a week.....	4
Rarely or never.....	5

25/

11. Which of the following best describes your urinary control during the last 4 weeks?

No urinary control whatsoever.....	1
Frequent dribbling.....	2
Occasional dribbling.....	3
Total control.....	4

26/

12. How many pads or adult diapers per day did you usually use to control leakage during the last 4 weeks?

None	0
1 pad per day.....	1
2 pads per day.....	2
3 or more pads per day.....	3

(Circle one number)

27/

13. How big a problem, if any, has each of the following been for you during the last 4 weeks?

(Circle one number on each line)

	No Problem	Very Small Problem	Small Problem	Moderate Problem	Big Problem	
a. Dripping or leaking urine	0	1	2	3	4	28/
b. Pain or burning on urination.....	0	1	2	3	4	29/
c. Bleeding with urination.....	0	1	2	3	4	30/
d. Weak urine stream or incomplete emptying.....	0	1	2	3	4	31/
e. Waking up to urinate.....	0	1	2	3	4	32/
f. Need to urinate frequently during the day	0	1	2	3	4	33/

14. Overall, how big a problem has your urinary function been for you during the last 4 weeks?

No problem.....	1
Very small problem.....	2
Small problem.....	3
Moderate problem.....	4
Big problem.....	5

(Circle one number)

34/

Urinary Symptoms
(Circle one number on each line)

	Not at all	Less than 1 time in 5	Less than half the time	About half the time	More than half the time	Almost always	
15. Incomplete emptying Over the past month, how often have you had a sensation of not emptying your bladder completely after you finished urinating?.....	0	1	2	3	4	5	35/
16. Frequency Over the past month, how often have you had to urinate again less than two hours after you finished urinating?.....	0	1	2	3	4	5	36/
17. Intermittency Over the past month, how often have you found you stopped and started again several times when you urinated?.....	0	1	2	3	4	5	37/
18. Urgency Over the past month, how often have you found it difficult to postpone urination?.....	0	1	2	3	4	5	38/
19. Weak Stream Over the past month, how often have you had a weak urinary stream?.....	0	1	2	3	4	5	39/
20. Straining Over the past month, how often have you had to push or strain to begin urination?.....	0	1	2	3	4	5	40/
21. Nocturia Over the past month, how many times did you most typically get up to urinate from the time you went to bed at night until the time you got up in the morning?	(none)	(1 x)	(2 x)	(3 x)	(4 x)	(5x or more)	41/

BOWEL HABITS

The next section is about your bowel habits and abdominal pain.
Please consider ONLY THE LAST 4 WEEKS.

22. How often have you had rectal urgency (felt like I had to pass stool, but did not) during the last 4 weeks?

More than once a day.....	1
About once a day.....	2
More than once a week.....	3
(Circle one number)	
About once a week.....	4
Rarely or never.....	5

42/

23. How often have you had uncontrolled leakage of stool or feces?

More than once a day.....	1
About once a day.....	2
More than once a week.....	3
(Circle one number)	
About once a week.....	4
Rarely or never.....	5

43/

24. How often have you had stools (bowel movements) that were loose or liquid (no form, watery, mushy) during the last 4 weeks?

Never.....	1
Rarely.....	2
About half the time.....	3
(Circle one number)	
Usually.....	4
Always.....	5

44/

25. How often have you had bloody stools during the last 4 weeks?

Never.....	1
Rarely.....	2
About half the time.....	3
(Circle one number)	
Usually.....	4
Always.....	5

45/

26. How often have your bowel movements been painful during the last 4 weeks?

Never.....	1
Rarely.....	2
About half the time.....	3
Usually.....	4
Always.....	5

(Circle one number)

46/

27. How many bowel movements have you had on a typical day during the last 4 weeks?

Two or less.....	1
Three to four.....	2
Five or more.....	3

(Circle one number)

47/

28. How often have you had crampy pain in your abdomen, pelvis or rectum during the last 4 weeks?

More than once a day.....	1
About once a day.....	2
More than once a week.....	3
About once a week.....	4
Rarely or never.....	5

(Circle one number)

48/

29. How big a problem, if any, has each of the following been for you? (Circle one number on each line)

	No Problem	Very Small Problem	Small Problem	Moderate Problem	Big Problem	
a. Urgency to have a bowel movement	0	1	2	3	4	49/
b. Increased frequency of bowel movements.....	0	1	2	3	4	50/
c. Watery bowel movements.....	0	1	2	3	4	51/
d. Losing control of your stools.....	0	1	2	3	4	52/
e. Bloody stools	0	1	2	3	4	53/
f. Abdominal/ Pelvic/Rectal pain...	0	1	2	3	4	54/

30. Overall, how big a problem have your bowel habits been for you during the last 4 weeks?

No problem.....	1
Very small problem.....	2
Small problem.....	3
Moderate problem.....	4
Big problem.....	5

(Circle one number)

55/

SEXUAL FUNCTION

The next section is about your **current** sexual function and sexual satisfaction. Many of the questions are very personal, but they will help us understand the important issues that you face every day. Remember, THIS SURVEY INFORMATION IS COMPLETELY CONFIDENTIAL. Please answer honestly about **THE LAST 4 WEEKS ONLY**.

31. How would you rate each of the following during the last 4 weeks? (Circle one number on each line)

	Very Poor to None	Poor	Fair	Good	Very Good	
a. Your level of sexual desire?.....	1	2	3	4	5	56/
b. Your ability to have an erection?.....	1	2	3	4	5	57/
c. Your ability to reach orgasm (climax)?.....	1	2	3	4	5	58/

32. How would you describe the usual **QUALITY** of your erections **during the last 4 weeks**?

None at all.....	1					
Not firm enough for any sexual activity.....	2					
Firm enough for masturbation and foreplay only.....	3	(Circle one number)				59/
Firm enough for intercourse.....	4					

33. How would you describe the **FREQUENCY** of your erections **during the last 4 weeks**?

I NEVER had an erection when I wanted one.....	1					
I had an erection LESS THAN HALF the time I wanted one.....	2					
I had an erection ABOUT HALF the time I wanted one	3	(Circle one number)				60/
I had an erection MORE THAN HALF the time I wanted one.....	4					
I had an erection WHENEVER I wanted one.....	5					

34. How often have you awakened in the morning or night with an erection **during the last 4 weeks**?

Never	1					
Less than once a week.....	2					
About once a week.....	3	(Circle one number)				61/
Several times a week.....	4					
Daily.....	5					

35. During the last 4 weeks, how often did you have any sexual activity?

Not at all.....	1	
Less than once a week.....	2	
About once a week.....	3	(Circle one number)
Several times a week.....	4	
Daily.....	5	

62/

36. During the last 4 weeks, how often did you have sexual intercourse?

Not at all.....	1	
Less than once a week.....	2	
About once a week.....	3	(Circle one number)
Several times a week.....	4	
Daily.....	5	

63/

37. Overall, how would you rate your ability to function sexually during the last 4 weeks?

Very poor.....	1	
Poor.....	2	
Fair.....	3	(Circle one number)
Good.....	4	
Very good.....	5	

64/

38. How big a problem during the last 4 weeks, if any, has each of the following been for you?

(Circle one number on each line)

	No Problem	Very Small Problem	Small Problem	Moderate Problem	Big Problem	
a. Your level of sexual desire.....	0	1	2	3	4	65/
b. Your ability to have an erection.....	0	1	2	3	4	66/
c. Your ability to reach an orgasm.....	0	1	2	3	4	67/

39. Overall, how big a problem has your sexual function or lack of sexual function been for you
during the last 4 weeks?

No problem.....	1	
Very small problem.....	2	
Small problem.....	3	(Circle one number)
Moderate problem.....	4	
Big problem.....	5	

68/

HORMONAL FUNCTION

The next section is about your hormonal function. Please consider **ONLY THE LAST 4 WEEKS**.

40. Over the last 4 weeks, how often have you experienced hot flashes?

More than once a day.....	1
About once a day.....	2
More than once a week.....	3
About once a week.....	4
Rarely or never.....	5

69/

41. How often have you had breast tenderness during the last 4 weeks?

More than once a day.....	1
About once a day.....	2
More than once a week.....	3
About once a week.....	4
Rarely or never.....	5

70/

42. During the last 4 weeks, how often have you felt depressed?

More than once a day.....	1
About once a day.....	2
More than once a week.....	3
About once a week.....	4
Rarely or never.....	5

71/

43. During the last 4 weeks, how often have you felt a lack of energy?

More than once a day.....	1
About once a day.....	2
More than once a week.....	3
About once a week.....	4
Rarely or never.....	5

72/

44. How much change in your weight have you experienced during the last 4 weeks, if any?

Gained 10 pounds or more.....	1
Gained less than 10 pounds	2
No change in weight.....	3
Lost less than 10 pounds	4
Lost 10 pounds or more.....	5

73/

45. How big a problem **during the last 4 weeks**, if any, has each of the following been for you?

(Circle one number on each line)

	No Problem	Very Small Problem	Small Problem	Moderate Problem	Big Problem	
a. Hot flashes.....	0	1	2	3	4	74/
b. Breast tenderness/enlargement..	0	1	2	3	4	75/
c. Loss of Body Hair.....	0	1	2	3	4	76/
d. Feeling depressed.....	0	1	2	3	4	77/
e. Lack of energy.....	0	1	2	3	4	78/
f. Change in body weight	0	1	2	3	4	79/

Overall Satisfaction

46. Overall, how satisfied are you with the treatment you received for your prostate cancer?

Extremely dissatisfied.....	1	
Dissatisfied.....	2	
Uncertain.....	3	(Circle one number)
Satisfied.....	4	
Extremely satisfied.....	5	

THANK YOU VERY MUCH!!

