5.1 Inclusion Criteria

Yes/No (Response of "no" = patient ineligible)

5.1.1 _____ Asymptomatic or symptomatic hormone naïve men with testosterone levels ≥ 100 ng/dL with previously treated localized prostate cancer who now have rising PSAs and five or fewer bone metastases.

5.1.2 _____ Subjects who have been previously treated with definitive and/or adjuvant/salvage radiotherapy to the primary site and/or regional lymph nodes with concurrent ADT are allowed if the last hormone therapy delivered > 6 months prior. Subjects who have had more than 30 days and fewer than 45 days of bicalutamide monotherapy for any reason within the 6 months prior to enrollment are eligible for the study, providing they have been off of the drug for at least 30 days prior to enrollment. Subjects who have had fewer than 30 days of bicalutamide are eligible for the study, as long as they discontinue the drug at least 5 days prior to the first study treatment.

5.1.3 _____ Histologic confirmation of Prostate Adenocarcinoma diagnosis.

5.1.4 _____ Age ≥ 18 years.

5.1.5 _____ Life expectancy of at least 2 years.

5.1.6 _____ Acceptable hematology and serum biochemistry screening values:

- White Blood Cell Count (WBC) $\geq 3,000/\text{mm}^3$
- Absolute Neutrophil Count (ANC) $\geq 1,500/\text{mm}^3$
- Platelet (PLT) count $\geq 100,000/\text{mm}^3$
- Hemoglobin (HGB) $\geq 10 \text{ g/dL}$
- Total bilirubin level $\leq 1.5 \times$ institutional upper limit of normal (ULN)
- Aspartate aminotransferase (AST) and alanine aminotransferase (ALT) $\leq 2.5 \times$ ULN
- Creatinine $\leq 1.5 \times$ ULN
- Albumin $> 2.5 \text{ mg/dL}$

5.1.7 _____ Willing and able to comply with the protocol, including follow-up visits and examinations.

5.1.8 _____ Karnofsky Performance Score >60 or ECOG equivalent.

5.1.9 Radiographic confirmation of oligometastatic diagnosis via Bone Scan validated by either CT scan, or MRI or PET/CT with Fluciclovine within the past 90 days.

5.1.10 Subjects who have not had surgical removal of their prostate and have a partner of child bearing potential must agree to use condoms beginning at the signing of the ICF until at least 6 months after the last dose of study drug. Because of the potential side effect on spermatogenesis associated with radiation, female partners of childbearing potential must agree to use a highly effective contraceptive method during and for 6 months after completing treatment.

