9 STUDY CALENDAR

1 cycle = 28 days¹¹

Examination	Screening ¹	Neo-adjuvant C1	EBRT	C2 ⁷	C3	C4	C5	C6	End of Treatment ¹⁷	Follow-up ⁸
Informed consent	X									
Medical history	X									
Eligibility criteria	X									
Vital signs	X	X		X	X	X	X	X	X	
Physical examination ¹⁸	X	X		X	X	X	X	X	X	X
Karnofsky Performance Status or ECOG Equivalent (Appendix 17.5) ¹⁸	X	X		X	X	X	X	X	X	
Concomitant Medications ¹⁸	X	X	X	X	X	X	X	X	X	X
Adverse Events ¹⁴		X	X	X	X	X	X	X	X	X
Hematology ^{2, 13}	X	X ¹³		X ¹³	X					
Chemistry ^{3, 13}	X	X ¹³		X ¹³	X					
ECG ⁵	X									
CT or MRI ⁴	X								X	
Radium-223 ¹⁶		X		X	X	X	X	X		
EBRT			X							
PSA and Testosterone ^{9, 13}	X	X	X ⁹	X	X	X	X	X	X	X
Bone scans ⁶	X			X ¹²	X ¹²	X	X ¹²	X ¹²	X	X
QOL questionnaires	X		X ¹⁵			X			X	X
Myriad CCP ¹⁰	X									
Myriad HRD ¹⁰	X									

- 1 ALL Pre-study/Screening procedures should be completed within 4 weeks of study enrollment - with the exception of laboratory tests which need to be completed within 2 weeks prior to study enrollment, and imaging assessments which must be completed within 90 days of enrollment. Consent may be signed \leq 45 days prior to cycle one day one.
- 2 Hematology includes CBC with differential and platelets.
- 3 Chemistry includes Albumin, Alkaline Phosphatase, Aspartate Aminotransferase, Alanine Aminotransferase, Total Bilirubin, Calcium, Carbon Dioxide, Creatinine, Chloride, Glucose, Potassium, Protein, Sodium, Urea Nitrogen. 4 CT-based scans (either Fluciclovine PET/CT or diagnostic CT) or MRI that includes the chest, abdomen and pelvis. A similar imaging modality (MRI or CT-based) used at screening is preferred, but not required at follow up evaluation. Diagnostic CT at follow-up is sufficient if PET/CT was used at screening. Disease assessment to be conducted by PCWG2 and RECIST 1.1 section 10.1.1.
- 5 ECG will be done only if medically indicated.
- 6 Bone scans should be obtained between cycle 3 and 4 of the study dependent on any dose delays that may extend cycle time. Bone scans should be performed 2-4 weeks after the final Radium-223 dose. Bone scans will also be performed at any sign of progression as defined in section 10.
- 7 Cycle 2 may be delivered concurrently with external beam radiation to the primary site. Therefore, cycle 2 will NOT be delayed to allow completion of the external beam radiation.
- 8 Follow-up visits will occur every 3 months (+90/-30 days) for an approximate duration of two years from the time patients are enrolled on the study.

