- 9 PSA and Testosterone within 24 hours prior to or after starting external beam radiation.
- 10 Correlative studies are OPTIONAL; refer to section 14.1 for archival tissue instruction
- 11 Cycles should occur at least 28 days after the previous cycle and no more than 42 days after the previous cycle (0 to +14 days).
- 12 Bone scans are optional at the time points indicated by this superscript and will be performed if there is clinical suspicion of progression that falls outside the objective criteria of progression for this study.
- 13 All post-screening laboratory tests should be drawn approximately 7 days, but no fewer than 3 business days, before radium dosing. Laboratory tests for CBC differential platelets must have results available prior to radium ordering. Laboratory safety assessments MUST be performed and resulted prior to radium dosing.
- 14 The collection of all adverse events will begin after the first dose of study treatment and end 30 days after the last dose of study treatment. The collection of treatment related adverse events will continue until the last study visit (or until new cancer treatment is initiated, if sooner).
- 15 QOL Questionnaires should be completed on the final day of EBRT \pm 7days.
- 16 If a patient meets biochemical progression, the patient may continue to receive treatment, at the Investigator's discretion, until a validated PSA test has confirmed biochemical progression.
- 17 End of treatment visit will occur 28 days (\pm 7 days) after last treatment is administered.
- 18 Physical exam, KPS or ECOG equivalent, and concomitant medications do not need to be repeated if they have been performed less than 7 days prior.

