Exploratory endpoints are to evaluate if a commercially available cell-cycle progression gene assay (Myriad CCP) performed on the original prostate biopsy or surgical pathology specimen correlates with biochemical or clinical progression free survival in the study population.

Correlations with survival endpoints will be performed using exploratory Cox proportional hazards regression analysis.

Primary analysis and report planned at 15 months of follow up for all enrollees.

Health-related Quality of Life as scored by EPIC urinary, bowel, sexual, and hormonal domains, as well as PROMIS-29 questionnaires.

Medians, ranges, and quartiles will be computed for all health-related Quality of Life domains. Exploratory logrank tests will be used to relate domain scores to survival outcomes (hormone-free survival, time to first skeletal event, overall survival, and PSA doubling time).

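### The only pre-treatment EPIC is at screening, so in men with recent bicalutamide the baseline hormonal and sexual scores can describe time on drug

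*Combined protocol and SAP*

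**What the plan says.** **Timing of the form.** In the Section 9 calendar, the row "QOL questionnaires" is marked at Screening, EBRT, C4, End of Treatment and Follow-up. The Neo-adjuvant C1 cell is empty. Footnote 15 fixes the EBRT form: "QOL Questionnaires should be completed on the final day of EBRT", within 7 days either way. Section 7.1.1 starts EBRT after the first radium cycle, so screening is the only pre-treatment EPIC. Footnote 1 sets its window: "ALL Pre-study/Screening procedures should be completed within 4 weeks of study enrollment". The same footnote allows consent up to 45 days before cycle 1 day 1.

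**Recall.** In Appendix 17.2 the sexual and hormonal sections both cover the last 4 weeks, for example "Over the last 4 weeks, how often have you experienced hot flashes".

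**Who may enter.** Section 5.1.2 admits two groups with recent bicalutamide:
- longer exposure (more than 30 and fewer than 45 days, within the 6 months before enrollment): "providing they have been off of the drug for at least 30 days prior to enrollment";
- shorter exposure (fewer than 30 days): "as long as they discontinue the drug at least 5 days prior to the first study treatment".

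**Analysis.** Section 11 states: "Medians, ranges, and quartiles will be computed for all health-related Quality of Life domains". It adds exploratory logrank tests relating domain scores to survival outcomes. It names no baseline visit, no change-from-baseline measure and no handling of prior bicalutamide.

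**The concern.** Objective 1.2.2 evaluates the EPIC hormonal and sexual domains. Section 2 argues for avoiding ADT by listing loss of libido, lack of energy and hot flashes, and these two domains ask about all three. They are the part of the QOL data closest to the trial's rationale.

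A baseline meant to show the man before study treatment may instead show him on an anti-androgen. If the drug depresses the score, stopping it would raise the later scores whatever the study regimen does. With one arm, no concurrent control can separate the two. The logrank tests could carry the same problem if they use the baseline score; the plan does not say which visit's score they use.

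**Working it through.** The plan gives no power, effect size or other figure for QOL, so there is none to reproduce. The check is a count of days.

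**Inputs**
- Recall: 28 days (Appendix 17.2).
- EPIC date: up to 28 days before enrollment (Section 9, footnote 1).
- Longer exposure: up to 44 days of drug, off at least 30 days before enrollment (5.1.2).
- Shorter exposure: up to 29 days of drug, off at least 5 days before first treatment (5.1.2).
- LHRH agents: excluded for the prior six months (5.2.2), so they cannot fall in the window.

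**Formula.** Let e be the days from the EPIC to the date at which the washout is counted, and w the minimum washout. The recall runs from day -(e + 28) to day -e, and the drug may run to day -w. The maximum overlap is
- 28 - (w - e), not below 0, when e < w;
- 28 when e ≥ w, since both permitted durations can exceed 28 days.

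**As planned**

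| Group | EPIC timing | Maximum on-drug days of 28 |
|---|---|---|
| Longer (w = 30) | 28 days before enrollment | 28 - (30 - 28) = 26 |
| Longer | 14 days before | 28 - (30 - 14) = 12 |
| Longer | 7 days before | 28 - (30 - 7) = 5 |
| Longer | day of enrollment | 28 - 30 < 0, so 0 |
| Shorter (w = 5) | 5 or more days before first treatment | 28 |

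**With the form at cycle 1, before the infusion (e = 0)**
- Longer: 0 of 28. This also holds if cycle 1 falls after enrollment.
- Shorter: 28 - 5 = 23 of 28 (82%).

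If the last dose may fall on day -30 or day -5 itself, and that day counts as a drug day, then 26, 12, 5 and 23 each rise by one; the 0 and 28 do not change.

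**Effect on the summary (illustration only).** Let k of 20 men be exposed, with a baseline deficit of d points each. The baseline mean is low by k × d / 20. The documents give neither k nor d. With d assumed to be 5 to 20 points:
- k = 0: shift 0;
- k = 1: 1 × 5/20 = 0.25 to 1 × 20/20 = 1 point;
- k = 4: 4 × 5/20 = 1 to 4 × 20/20 = 4 points;
- k = 8: 8 × 5/20 = 2 to 8 × 20/20 = 8 points.

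Simulated medians (20 men, normal scores, mean 70, SD 15 or 25) shift by similar amounts. At d = 20 they shift by 0.8 to 0.9, 3.4 to 3.8 and 7.7 to 7.9 points for k = 1, 4 and 8. The full deficit is applied to every exposed man, however many of his recalled days were on drug, so these figures lean high.

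**The case against.** A reader might infer that washout will show up as a QOL gain and that the QOL result is biased in favour of the regimen. The documents do not support that, for four reasons.

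1. They say nothing about EPIC scores on a few weeks of bicalutamide alone. The only QOL decrement stated is for long-term ADT (Section 2). Direction and size are both assumed.
2. No planned analysis computes a gain. Secondary endpoints are descriptive, and Section 4.1 speaks of better QOL against the SWOG historic cohort, not against baseline. A false gain needs someone to compare summaries across visits.
3. Over the whole study the net direction is open. Men who progress still complete all questionnaires (Section 7.4), and even the alternative hypothesis has 80% starting systemic therapy by 15 months. On Section 2's premise, ADT starts would pull later scores down.
4. The day counts are maxima. The 26 days need the drug stopped at the limit and the form completed on the first permitted day; at 7 days before enrollment the maximum is 5.

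All four stand. They limit the point to exposed men, and mainly to the EBRT, C4 and end-of-treatment forms. They do not remove the mechanism: the schedule permits it, and comparing visits is a natural use of medians reported at five scheduled time points.

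A further objection is that moving the form does little for the shorter-exposure group. That is also right, and it is why the with-and-without summary leads the remedy. For men with no bicalutamide, a recall window that ends some weeks before dosing is an ordinary screening baseline, and no bias follows from it.

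**Conclusion.** The point holds in limited form. The only baseline EPIC may cover bicalutamide time for at most 26 of 28 days (longer exposure) or 28 of 28 days (shorter exposure), because neither washout is tied to the date of the form. This could make recovery from the drug look like benefit, or like absence of harm, in the early QOL summaries.

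That consequence rests on two things the documents do not supply: that some enrolled men had recent bicalutamide, and that it lowers their hormonal or sexual scores. If either fails, there is no such artefact. The point ranges above are illustrations, not estimates. The endpoint is secondary and descriptive, and the primary test is not touched. This is a minor improvement, worth making because it costs so little.

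**What to change.** 1. **Section 11, one sentence.** Report the EPIC hormonal and sexual summaries, at baseline and at each later visit, with and without men whose 28-day baseline recall includes bicalutamide days, and state how many such men there are. The stop date is already needed to verify 5.1.2. This is the part that deals with the shorter-exposure group, and it can be applied to men already enrolled.
2. **Section 9, one calendar cell.** Move the baseline QOL mark from Screening to Neo-adjuvant C1, completed before the infusion, and define that form as baseline. The man already attends, and QOL is not an eligibility item. For men already treated, a pre-infusion form cannot be recovered.

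The cost is one sentence, one cell and a small subset table, with no added visit or form. The downside is that a man who consents but never reaches cycle 1 will have no QOL form. No eligibility or washout rule needs to change.
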